**Table 2: Clinical Protocol Procedures**

At prostatectomy, the fresh prostate gland will be processed. The custom-made 3D mold, created for the individual patient with MRI data, will be used to guide placement of the “post treatment biopsy”, which is actually a sampling of the prostatectomy specimen in the exact geometric location as the pre-treatment biopsy. The fresh prostatectomy specimen will be placed in the mold and the one or two core samples obtained will be handled as described above. Documentation of precise location of the biopsy will be recorded with appropriate coordinates, and location will be correlated with the subsequent cutting of tissue cross sections. Then, the tissue will be processed by NCI Laboratory of Pathology staff for diagnosis and pathology report generation. The cross sections will be labeled and will be cut into halves or quadrants for routine histology processing, while documenting which cross section and quadrant (right anterior #1, left posterior #1, etc.) from which they originated. This will serve as a guide to the location of the post treatment biopsy, as that location will have been recorded keeping in mind the cross section number. After the prostatectomy specimen has been signed out by the Pathology Department

with final diagnosis and report issued, correlation between the post treatment biopsy and the whole section will occur. The tissue section(s) from which the post treatment biopsy was taken will be analyzed morphologically and compared to the biopsy. If indicated, the block or blocks of the slides to be compared can be sectioned further for complete morphologic analysis of presence/absence of residual tumor, tumor grade, tumor extent, etc.

MR 2 data will be performed according to the specialized protocol reported previously. [17, 23] All tumor foci will be re-identified. The 3D mold will provide target localization and trajectory path for post prostatectomy core biopsies.

Prior to prostatectomy we will use the MRI data and resulting 3D custom built molds of the entire prostate gland and foci of tumor within it. [29] Focal tumors and all prior biopsy targets will be re-identified where possible and mapped on MR imaging. This allows for image-based targets and/or regions registered from baseline MR exam to be re-identified for repeat biopsy. This second set of biopsies will be taken after gland removal. The core needle biopsies will be taken before specimen fixation and pathological analysis. These cores will be taken from the pre-defined locations identified on MR and displayed in the 3D mold. Most importantly this will provide tissue samples from *the same locations* both before and after therapy and allow for sampling of sub regions of activity within the lesion based upon the mpMRI appearances. The prostate specimen can be whole mount sectioned in a customized mold, allowing geometric alignment to magnetic resonance imaging and therefore precise comparison of MRI/pathologic response. The prostate specimen, after the core needle biopsy samples have been removed, the specimen will be processed in the routine way with full histo-pathological and genomic analysis.

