## 1.11 IMAGING

### 1.11.1 mpMRI pre and post preoperative goserelin and enzalutamide

[figure not shown]
Patients will undergo pre-therapy ecoil MRI at 3T at screening. All MR data sets will be reviewed for quality and completeness. DCE PK analysis will be performed using commercially available iCAD software (<http://www.icadmed.com>). Post 6 months of preoperative therapy, a second ecoil MRI at 3T will be obtained. At both time points, quantitative T2, ADC values and DCE metrics will be extracted and recorded from all foci. DCE metrics to be collected include empirical indices such as Area Under the Curve at 90 seconds (AUC90) and Time to Peak (TTP), and also the derived indices  $K^{\text{trans}}$  (the forward volume transfer constant of Gadolinium between blood plasma and the interstitial space, expressed in units of  $\text{min}^{-1}$ ), and  $v_e$ , the dimensionless fractional volume of interstitial or extracellular space per unit volume of tissue. In addition, PiRads data will be collected for both time points.

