### 1.11.2 Registration of pre- and post-therapy prostate MRIs

Drs. [name], [name], and [name] will collaborate on evaluation and registration of pre- and post-treatment MRIs. We will use non-rigid image registration for establishing correspondence between the targets and sub-areas in the baseline and post-therapy MR images. Preoperative therapies are known to significantly alter MR signal signatures for both normal and tumor tissue. [25, 26] We expect large reduction of the prostate gland from the baseline to post-treatment imaging session. These issues undoubtedly make the registration problem very challenging. Based on the limited preliminary evidence, intensity-based deformable registration based on Mutual information similarity metric pioneered by our group [27] can be used for co-registration of pre- and post-treatment prostate MRI. Our early preliminary results show the feasibility of such registration for the data collected in preoperative therapy cases (see [Figure 5](#) below). A

variety of deformable registration methods based on Mutual Information are available in 3D Slicer, [28] and will be applied to this problem. The transformations derived by the registration will be used to map the areas in the pre-treatment scans to the post-treatment gland configuration. This information will be used in manufacturing the custom mold that will include needle access to the image-registered locations of lesions to collect tissue samples from the ex vivo specimen.

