**1.17.1 Histopathological Analysis**

After localization by MR of the desired pretreatment and post treatment biopsy sites, one or two immediately adjacent tissue cores will be obtained from the lesion. One core will be placed in formalin (FFPE) for processing for histopathology, to confirm tumor diagnosis, Gleason grade and extent of tumor. The second core, if obtainable (presumed to be nearly identical in features to the first core), will be reserved for molecular analyses detection of androgen receptor variants. This analysis will be done only if there is sufficient tissue and after obtaining informed consent.

Clinical protocol steps	Procedures	Core pathology analyses
Pre-treatment (MR 1): MRI Index lesion(s) identified	In vivo Biopsy  Index lesion(s)  Optional biopsy	#1: FFPE (histology)  #1A FFPE & 1 H&E (molecular analyses)  #2: Fresh frozen (optional)
ADP Therapy	Prostatectomy	Full pathology report issued
Post-treatment (MR 2): MRI Index lesion(s) identified (same lesion(s) as above)	Ex Vivo Biopsy  Index lesion(s)  Optional biopsy	#1: FFPE (histology)  #1A FFPE & 1 H&E (molecular analyses)  #2: Fresh frozen (optional)

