## **STATISTICAL CONSIDERATIONS**

The primary objective of this exploratory trial is to obtain pilot data to assess the utility and role of mpMRI in localization and detection of focal prostate cancer both before and after treatment with pre-operative ADT and enzalutamide. Secondary objectives include obtaining pilot data to guide future studies with respect to determining genetic predictors and correlates of response to therapy as well as to link imaging information to genomic information related to resistance.

Patients who have newly diagnosed prostate cancer will undergo treatment with androgen deprivation therapy and enzalutamide and will undergo mpMRI imaging at screening and 6 months. The imaging will be used to monitor the changes in the individual tumors located within the prostate. As these patients will all have multiple tumors within the prostate, it is anticipated that approximately 25% of the patients will experience minimal declines in tumor and still have significant residual disease, 25% may have complete disappearance of tumor, and the remainder will show substantial improvement (disappearance of some lesions, with others being much smaller). To guide sample size determination, it is estimated that for an exploratory investigation of the association of genomic information and its relationship to response, it would be useful to have at least a minimum of 10 patients who still have significant residual disease in order to form preliminary assessments of the relationships noted. As such, if 50 total evaluable patients were to enroll on the trial and if the probability of being in this category was 25%, there would be 83.6% probability of having at least 10 such patients. Thus, this pilot study will plan to enroll 50 total evaluable patients who would all undergo primary treatment and mpMRI imaging to assess the role of imaging in this setting. The accrual ceiling will be 55 in order to accommodate a small number of patients who may be inevaluable. Successful use of this imaging will lead to analyses related to the association with genomic traits at baseline and prostatectomy and whether there is disappearance of tumor or not. On this trial, all of these investigations will be performed with exploratory, hypothesis generating intent.

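### Does promising to re-identify every tumor focus on the second MRI undermine the post-treatment detection result?

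*Combined protocol and SAP*

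**What the plan says.** The primary objective (1.1.1) is the feasibility of mpMRI for localizing and detecting focal cancer before and after treatment.

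- **Second MRI, unqualified.** Section 1.17.1, under Table 2: "All tumor foci will be re-identified". The Table 2 row for this scan reads "MRI Index lesion(s) identified (same lesion(s) as above".
- **Second MRI, qualified.** The next paragraph of the same section: "Focal tumors and all prior biopsy targets will be re-identified where possible and mapped on MR imaging". It continues: "This allows for image-based targets and/or regions registered from baseline MR exam to be re-identified for repeat biopsy".
- **Registration.** Section 1.11.2: "The transformations derived by the registration will be used to map the areas in the pre-treatment scans to the post-treatment gland configuration".
- **Measurements.** Section 1.11.1: "At both time points, quantitative T2, ADC values and DCE metrics will be extracted and recorded from all foci". PI-RADS data are also collected at both scans.
- **Expected response.** Statistical Considerations starts from "As these patients will all have multiple tumors within the prostate". It anticipates minimal decline in about 25% of men, and for the others "25% may have complete disappearance of tumor, and the remainder will show substantial improvement (disappearance of some lesions, with others being much smaller".
- **Entry.** Criterion 1.3.1.11 requires lesions that MRI can detect for biopsy, and 1.3.1.1 requires confirmed cancer.

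**The concern.** Two rules appear to govern one step. One says that every focus is found again. The other says this happens only where it can, and the sample-size section expects many foci to be gone. If a location carried over by registration counts as re-identified, the post-treatment rate is 100% whatever the scan shows. If only visible lesions count, the rate could be about half. Since detection after treatment is part of the primary objective, an undefined term seems able to decide the answer.

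The same ambiguity could reach the genomic work. Tissue from a lesion that persisted and tissue from a mapped site where the lesion vanished might both be called re-identified, which would blur the contrast between resistant and responsive tumor.

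At baseline, every enrolled man is MRI-positive by selection, so patient-level detection before treatment carries no information.

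**Working it through.** **1. The plan's own figure.** Inputs from Statistical Considerations: n = 50 evaluable men, probability 0.25 of significant residual disease, at least 10 such men wanted. P(X ≥ 10) for X ~ Binomial(50, 0.25) is 0.8363, which matches the stated 83.6%. Nothing below alters it.

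**2. How far the unqualified sentence is from the expected response.** The split is 0.25 minimal decline, 0.25 all gone, and 1 − 0.25 − 0.25 = 0.50 some gone.

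- Men losing at least one lesion: 0.25 + 0.50 = 0.75, and 50 × 0.75 = 37.5 (95% binomial range 31 to 43).
- Probability that no man has complete disappearance: 0.75^50 = 5.7 × 10⁻⁷.

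Read as a statement about visible lesions, the sentence is incompatible with the plan's expectation.

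**3. Share of baseline lesions still visible.** Assume that men with minimal decline lose no lesion. Lesions per man are also assumed, within the multiple tumors that the plan expects and its limit of three index lesions (1.8).

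- Two per man, partial responders keep one: (0.25 × 2 + 0.50 × 1)/2 = 0.50, or 50 of 100.
- Three per man, partial responders keep one: (0.25 × 3 + 0.50 × 1)/3 = 0.417, or 62.5 of 150.
- Three per man, partial responders keep two: (0.25 × 3 + 0.50 × 2)/3 = 0.583, or 87.5 of 150.
- Weaker response (assumed 0.10 all gone, 0.25 some gone, 0.65 none gone): 0.775 with two per man, and 0.733 to 0.817 with three.

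**4. What that share measures.** Take two lesions per man and suppose the disappearance is real. Of 100 baseline lesions, 50 remain: 12.5 men × 2 = 25, plus 25 men × 1 = 25. A perfect scan sees all 50. Against residual tumor it scores 50/50 = 100%; against baseline lesions it scores 50/100 = 50%. A scan with sensitivity s for residual tumor would score 0.50 × s on the baseline denominator. That denominator mixes response with detection, so neither 100% by registration nor about 50% by visibility says whether MRI still finds tumor after therapy.

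**5. Whether the plan uses a re-identification rate.** It does not. The unqualified sentence stands in Biospecimen Collection, immediately before the mold's role in targeting the cores. The same section describes the post-treatment biopsy as sampling the specimen at the location of the pre-treatment one. The text with Figure 4 gives making the mold as the main purpose of the second scan. In this setting, re-identifying a focus means finding where to put the needle.

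**6. What the plan has for detection.** Section 1.17.1 assesses residual tumor in the sections from which the cores came and provides for mold-guided whole-mount sectioning aligned to MRI. Section 1.17.9 compares pathology with imaging.

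**7. Baseline.** Positivity is 50/50 by criterion 1.3.1.11. If the targeted biopsy also supplied the diagnosis, selection would raise an assumed true target yield of 70% to 0.70/(1 − 0.30^n) = 100%, 77% or 72% for n = 1, 2 or 3 independent targets. The 70% is not in the documents, and the 100% needs a single target per man, whereas the plan expects several tumors.

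**The case for a change.** The strongest case for a change is that the conflict is real and would be cheap to remove. The two sentences do differ, the term has no definition, and no unit, denominator or rule for a vanished lesion is given. Whether a lesion was visible is best judged before the registered map is overlaid, and such a judgment is hard to recover afterwards. Exploratory intent does not make an ambiguous record harmless.

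The difference in wording and the missing definition stand. The consequences claimed for them are much weaker:

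- The qualified sentence is in the next paragraph and already names two kinds of target, those seen on imaging and those carried over by registration. An analyst has the distinction to hand.
- For the genomic comparison within a patient, 1.8 requires areas that are both confirmed on pathology and unresponsive on MRI. A mapped site whose lesion has vanished does not qualify.
- Measuring a mapped region at the second scan is the correspondence that 1.11.2 sets out to establish, and PI-RADS at both scans bears on what was seen.
- The percentages in Statistical Considerations are anticipations about tumor. They follow a sentence on imaging but do not say outright that the disappearance is on MRI.

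The baseline point is correct as a limit on interpretation. However, no section promises patient-level sensitivity, specificity or negative predictive value, and paired sampling of one location needs a visible target, so the criterion should stay. Nor could lesion-level baseline sensitivity safely be labelled an upper bound. Registration error, in a problem that 1.11.2 itself calls very challenging, can also make a detected lesion look missed.

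**Conclusion.** No change to the plan is needed. The unqualified sentence is loose drafting in a tissue-sampling procedure. The paragraph after it supplies the qualification, and the expected response (about 37.5 of 50 men losing at least one lesion) shows which reading the authors must intend. The contrast between 100% and about half concerns a rate that the plan neither defines nor reports, and the half would be the score of a perfect scan if the plan's expected disappearances are real. Counting visible baseline lesions as the detection result would therefore add a misleading measure.

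A careful analyst will separate lesions seen on the second scan from sites located by registration, judge post-treatment detection against residual tumor in the specimen, and not present 50/50 baseline positivity as MRI performance. The plan supplies the material for each of these.

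This rests on the stated exploratory, hypothesis-generating intent, on the absence of any re-identification endpoint, and on the pathology-to-imaging comparison being carried out as described. The lesion-level shares depend on the assumed two or three lesions per man; the conclusion does not. The sample size and the 83.6% stand.

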### 1.17.2 Immunohistochemistry

The Laboratory of Pathology and the Warren G. Magnuson Clinical Center will perform Immunohistochemistry on biopsied tissue, if the patient elects to have the procedure. Immunohistochemistry of these tissue specimens will be obtained for CD4, CD8, and FOX-P3. In addition, phenotypic analysis of infiltrating immune cells will be performed.

### **1.17.3 Next-Generation Sequencing and Genomic Analysis**

Prostate cancer genomics are markedly heterogeneous, even within an individual focus. Genomic heterogeneity is associated with therapy resistance in multiple studies, and it is hypothesized that existing subclones comprise subclonal resistance effectors. Alternatively, the acquisition of new genomic alterations may confer a resistance phenotype to tumor cell clones or subclones. The analysis of tumor genomics both before therapy and after completion of neoadjuvant therapy can elucidate molecular features of resistant effectors and indicate if they arose through enrichment of intrinsic heterogeneity or acquisition of new alterations. Whole genome and/or exome sequencing will be performed on DNA isolated from matched core biopsy samples (MR1.1a and MR 2.1a). DNA taken from the buffy coat (see section on ctDNA) or benign adjacent prostate tissue will be used for a reference sample from which somatic alterations are identified. Germline analysis of DNA for inherited alterations reveal valuable insight into mechanisms of disease and will only be used for this purpose. Additionally, DNA may be isolated from involved tissue in the prostatectomy specimen after completion of clinical diagnostic evaluation by the Laboratory of Pathology, as described above. DNA sequencing and genomic analysis will be done using approved protocols under the auspices of Drs. [name] in the Laboratory for Genitourinary Cancer Pathogenesis, CCR.

#### *Sample Collection*

Pretreatment screening biopsy samples will be received by Laboratory of Pathology and processed in standard fashion using formalin fixation and paraffin embedding. Post-treatment biopsy samples will be obtained by Laboratory of Pathology and processed in standard fashion using formalin fixation and paraffin embedding, as described above. Biopsy samples and, if appropriate, adjacent areas of the prostatectomy specimen, will be used for molecular studies after completion of clinical diagnostic evaluation. To enrich for tumor cell purity, it is expected tumor specimens will undergo microdissection prior to isolation of DNA and preparation of sequencing libraries.

### **1.17.4 Circulating Tumor DNA (ctDNA)**

Circulating tumor DNA (ctDNA) is shed into the bloodstream by cells undergoing apoptosis or necrosis and in patients a proportion of the fragmented DNA in circulation is derived directly from the tumor. In recent years, ctDNA has shown promise as a non-invasive sensitive biomarker of tumor burden, and hence has potential as both a prognostic and surrogate response biomarker. In a study to detect ctDNA across 14 tumor types that had not yet metastasized or released detectable circulating tumor cells, ctDNA was detected at relatively high concentrations in the patients with metastatic cancer and at lower but detectable concentrations in those with localized cancers.[\[30\]](#) Together, these findings suggest that ctDNA could be a reliable biomarker for early detection as well as for determining optimal treatment, and monitoring resistance. ctDNA is abundant and readily detectable in most patients with advanced cancer; in cases with lower levels of ctDNA such as in early stage disease or minimal residual disease, detection is made possible with the use of advanced genomic methodologies. The analysis of ctDNA has considerable potential in the assessment of molecular heterogeneity, for monitoring

**Abbreviated Title:** Neoadjuvant ADT & Enzalutamide

**Version Date:** 01/25/2024

tumor dynamics, identifying genetic determinants of therapy, and evaluating treatment response; as well as detecting acquired resistance and developing potential strategies to circumvent this.[\[31\]](#) A recent study found that genomic analysis of ctDNA in plasma of mCRPC patients treated with abiraterone and enzalutamide identified key aberrations that may be associated with therapeutic resistance.[\[32\]](#) This data will be for research purposes only and will not be shared with patients.

#### *Sample Collection*

A baseline blood sample will be collected at the start of study and serial blood samples will be collected during the course of treatment at q3months, and at the end of study. Blood samples will be collected in 2 10-ml Streck Cell-Free DNA tube at room temperature and delivered to [name] lab for barcode labeling and/or processing and then [name] by Clinical Center Messenger Escort Service using a CRIS order. Processing and/or sequencing of plasma for ctDNA analysis will be performed by the Laboratory of Genitourinary Cancer Pathogenesis ([name]).

#### **1.17.5 Androgen Receptor Variants**

Detection of androgen receptor variants in tissue samples will be performed on one-half of one core biopsy to isolate total RNA from screening biopsy and radical prostatectomy specimens. RNA will be reverse transcribed and full-length androgen receptor (AR with LBD) as well as androgen receptor variants 5, 6, 7, 8 (V5-V8) will be detected by droplet digital PCR. This analysis will be performed when logistically feasible and only if there is sufficient tissue available.

#### *Sample Collection*

A baseline and post-treatment tumor sample will be collected, if feasible. Notify [name]'s lab in advance of the scheduled procedure by email. At the time of the procedure, please notify [name] lab by phone at [contact]. A member of [name] lab will be present for the procedure to collect the sample, if available. [name] lab will provide the collection media.

#### **1.17.6 Peripheral Blood microRNA and mRNA**

MicroRNA will be isolated from plasma and analyzed using Exiqon microRNA PCR panels. AR full-length (with the LBD) and splice variants will be assayed from CTCs isolated from peripheral blood drawn into two 10-ml lavender top tubes and from RNA purified from blood collected in one 2.5-ml PAXgene tube. The copy number of splice variants will be quantified using droplet digital PCR and a comparison performed between PAXgene and CTC-enriched samples. This sample will be collected only when logistically feasible

